9.4 Database management and quality control

Novartis personnel (or designated CRO) will review the data entered by investigational staff for completeness and accuracy. Electronic data queries stating the nature of the problem and requesting clarification will be created for discrepancies and missing values and sent to the investigational site via the EDC system. Designated investigator site staff are required to respond promptly to queries and to make any necessary changes to the data.

Concomitant treatments and prior medications entered into the database will be coded using the WHO Drug Reference List, which employs the Anatomical Therapeutic Chemical classification system. Medical history/current medical conditions and adverse events will be coded using the Medical dictionary for regulatory activities (MedDRA) terminology.

[REDACTED]

For EDC studies, after database lock, the investigator will receive a CD-ROM or paper copies of the patient data for archiving at the investigational site.

10 Statistical methods and data analysis

All data will be analyzed by a designated CRO in collaboration with Novartis. Any data analysis carried out independently by the investigator should be submitted to Novartis before publication or presentation. The data from all centers that participate in this study will be combined in the final safety and efficacy analysis.

10.1 Analysis sets

10.1.1 Full Analysis Set

The Full Analysis Set (FAS) will include all patients who have received at least one dose of study drug.

FAS will be used for the analysis of efficacy endpoints.

10.1.2 Safety set

The Safety Set will include all patients who received at least one dose of study treatment and had at least one post-baseline safety assessment.

Please note: the statement that a patient had no adverse event (on the Adverse Event eCRF) constitutes a safety assessment.

10.2 Patient demographics/other baseline characteristics

Demographic and other baseline data (including disease characteristics) will be listed and summarized for all patients using the FAS. Categorical data, such as gender, race, etc., will be presented by frequencies and percentages. For continuous data, mean, standard deviation, median, minimum, and maximum will be presented.

Relevant medical histories and current medical at baseline will be summarized for all enrolled patients.

10.3 Treatments (study treatment, concomitant therapies, compliance)

10.3.1 Study medication

Duration of study treatment exposure, cumulative dose and dose intensity will be summarized by the patient cohorts as above using the Safety Set. The number of patients with dose changes/interruptions will be presented along with reasons for the dose change/interruption. The safety set will be used for the tables and listings.

[REDACTED]

10.3.1 Concomitant therapies

Concomitant medications and significant non-drug therapies taken concurrently with the study drugs will be listed and summarized for the FAS by Anatomical Therapeutic Chemical Classification System (ATC) term, preferred term and treatment arm by means of frequency counts and percentages. These summaries will include medications starting on or after the start of study treatment (defined as cycle 1 day 1) or medications starting prior to the start of study treatment and continuing after the start of study treatment.

Any prior concomitant medications or significant non-drug therapies starting and ending prior to the start of study treatment will be listed. The safety set will be used for all above mentioned concomitant medication tables and listings.

10.4 Primary objective

The primary objective is to assess the clinical benefit of treatment with PDR001 + LAG525 at 24 weeks of treatment based on local investigator assessment.

For patients with solid tumors, the assessment criteria will be RECIST 1.1 and will include responses of CR or PR or SD. For lymphoma the Revised Response Criteria for Malignant Lymphoma (Cheson et al 2007) criteria will apply. Response criteria are included in the appendices.

For solid tumors, an assessment of CR or PR using RECIST 1.1 must be confirmed at least 4 weeks after initial observation. If the two assessments differ, the best overall response will be determined by Table 14-3 of [Appendix 1](#).

For efficacy parameters, data will be listed, summarized, or analyzed by tumor cohort.

10.4.1 Variable

The primary efficacy variable is the clinical benefit rate (CBR) (e.g. defined as CR, PR or SD) at week 24 by RECIST 1.1 for solid tumors and the Revised Response Criteria for Malignant Lymphoma, ([Cheson et al 2007](#)), for Lymphoma.

10.4.2 Statistical hypothesis, model, and method of analysis

The study will enroll patients from 7 tumor cohorts.

These seven pre-specified tumor cohorts (also referred to as “groups”) are:

Group	Malignancy
1	Small cell lung cancer
2	Gastric/esophageal adenocarcinoma
3	Castration resistant prostate adenocarcinoma (CRPC)
4	Soft tissue sarcoma
5	Ovarian adenocarcinoma
6	Advanced well-differentiated neuroendocrine tumors*
7	Diffuse large B cell lymphoma (DLBCL)*

We let Y_i be the response indicator for the i^{th} subject, and let R_g be the assumed probability of response within a control population and $\pi_g = \Pr(Y_i = 1 | g_i = g)$ be the underlying probability of response for group g within the trial. We transform to the logit scale for modeling purposes. Let θ_g be the mean log odds treatment effect, i.e.:

$$\theta_g = \log\left(\frac{\pi_g}{1 - \pi_g}\right) - \log\left(\frac{R_g}{1 - R_g}\right)$$

Thus, θ_g is the group specific logistic regression coefficient for group g . The primary analysis is a set of group specific tests that $\theta_g > 0$, meaning that the treatment is better than the assumed control rate for that group. Thus, we wish to test the set of hypotheses

$$H_{0g} : \theta_g \leq 0$$

$$H_{1g} : \theta_g > 0$$

We proceed in a Bayesian fashion, assigning a prior distribution (discussed below) and computing the posterior probability of H_{1g} within each group g . If, at the final analysis,

$$\Pr(\theta_g > 0 | \text{data}) > 0.80$$

then group g will be declared a success. Hence, the final analysis produces a separate decision for each group. The trial allows for early stopping of groups for futility, described below. No early stopping for success is allowed.

The statistical design borrows information across subgroups with a hierarchical model. The hierarchical model allows dynamic borrowing of information between groups such that more borrowing occurs when the groups are consistent and less borrowing occurs when the groups differ. In this way, the model is a compromise between the extremes of a completely pooled analysis as opposed to a separate analysis in each group. We additionally incorporate a clustering mechanism that allows borrowing within clusters but treats clusters separately. This minimizes borrowing across groups that are quite different in terms of CBR effects.

The hierarchical model approach involves two stages. The goal of both stages is to allow the data to drive the amount of borrowing across groups. If the data indicate a large amount of borrowing is appropriate (due to similar results), the model will borrow more and thus increase the overall power of the trial within each group. In contrast, if the data indicate a small amount of borrowing is appropriate (due to dissimilar results) the model will adjust and each group will stand more on its own. This “dynamic” borrowing property is distinct from other approaches which use a fixed informative prior or apriori assume an amount of borrowing across groups. Here the approach includes two stages to identify the appropriate amount of borrowing based on the data.

The first stage of model places the groups into distinct clusters. The purpose of this stage is to minimize borrowing of information across groups that appear to be quite different. Thus, for example, should 2 of the groups appear similar while the others differ significantly, the model may place a large probability on two clusters, one containing the two similar groups with the

other containing the remaining groups. The model does not pick one particular clustering, but instead incorporates the uncertainty of the data in this determination, producing a probability distribution over the possible clustering. Thus, in our example, the model may consider it highly likely that the 2 similar groups are in one cluster with the remaining groups in another, but it would also retain lower probabilities on the possibility all groups are in one cluster (e.g. we are simply seeing differences in the two groups by chance) as well as other possibilities. The complete analysis averages over this uncertainty.

At the second stage, we place hierarchical models over the groups within each cluster (thus, conditional on the clustering, there is no borrowing of information across clusters, only within clusters). The hierarchical model assumes that the θ_g have an across groups distribution

$$\theta_g \sim N(\mu, \tau^2)$$

The across group mean μ and variance τ^2 are unknown, and hence have a prior distribution which is combined with the data to produce estimates of μ and τ^2 .

The variance component τ controls the degree of borrowing among groups. Small values of τ result in a greater degree of borrowing while large values of τ correspond to less borrowing. The parameter τ is estimated using the data, so the observed between group variation is a key component of the model behavior.

Combined, the two stages allow groups with similar results to borrow information between them (they will have a high probability of being in the same cluster) while groups with different results will borrow far less information between them (they will have a low probability of being in the same cluster).

Details of the hierarchical model is provided in Appendix 4.

10.4.3 Evaluation of trial success and futility

Interim monitoring will occur once 5 subjects have CBR data available within a cohort. Interim analyses will continue every 3 months thereafter provided at least 10 subjects contribute new CBR data to the subsequent interim. Simulation studies in this document approximate this interim plan, as they are timed 12 weeks apart without any restrictions on the number of new observations within the analysis.

At each interim analysis, the groups will be evaluated for early futility and sample size expansion by comparing posterior quantities for the CBR to pre-specified early stopping criteria.

Table 10-1 Historical CBR for each group

Group Index	Tumor Type	Median PFS (mo.)	Hist. CBR (%)	Hypothetical Yearly Average Accrual (Subjects)
1	SCLC	1.5	6.25	20
2	Gastroesophageal	5	43.50	16
3	STS	6.2	51.10	13
4	Prostate	4	35.40	11
5	Ovarian	3	25.00	10

6	Advanced NET	5	43.50	7
7	DLBCL	3	25.00	6

Early Futility

If there is less than 20% probability that the response rate in a subgroup exceeds the historical rate R_g , then the group will stop enrollment early for futility. Formally, enrollment will stop early for futility if:

$$\Pr(\pi_g > R_g) < 0.20.$$

A group is only eligible for early stopping once a minimum of 5 patients have been evaluated for response in that group.

Early Success

If there is at least 70% probability that the response rate in a subgroup exceeds the historical rate, then the subgroup will stop enrollment early for success. Formally, enrollment will stop early for success if:

$$\Pr(\pi_g > R_g) > 0.70.$$

A minimum of 5 subjects will need to be evaluated prior to declaring a group to be efficacious. This eligibility remains effective until the next interim analysis is conducted, at which point eligibility is re-evaluated based on the currently available data and corresponding model outcomes.

Post-Expansion Futility

If there is less than a 60% probability that the clinical benefit rate in a group exceeds the historical rate, then the group will stop enrollment early for futility. Formally, enrollment will stop early for futility if:

$$\Pr(\pi_g > R_g) < 0.60.$$

A group is only eligible for this post-expansion stopping criterion once the group has expanded to a sample size beyond 10 subjects enrolled. Note this post-expansion futility is a stricter futility rule than that used prior to sample size expansion.

Final Analysis

The final analysis will occur when both accrual and follow-up are complete for all groups. If, at the completion of the trial, there is at least 80% probability that the response rate in a group exceeds the historical rate, then the group will be considered a success. Formally:

$$\Pr(\pi_g > R_g) > 0.80.$$

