5.2 Sample Size Expansion

If there is at least 70% probability that the clinical benefit rate in a group exceeds the historical rate, then the group is eligible to expand its overall sample size from 10 to 24 subjects. Formally, a group is eligible to expand if, at the last conducted interim:

$$\Pr(\pi_g > R_g) > 0.70.$$

A group is only eligible for sample size expansion once a minimum of 5 subjects has been evaluated for CBR in that group. This eligibility remains effective until the next interim analysis is conducted, at which point eligibility is re-evaluated based on the currently available data and corresponding model outcomes.

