6.3.2 Sample Size Expansion

The probability of expanding from an overall sample size of 10 to 24 is examined for each group within each scenario (Table 6, Figure 8). Groups that are in truth effective tend to have large probabilities of expanding to n=24 subjects (68%-90%). For scenarios in which there are only a few effective groups ('2 Great'), the probability of expanding those groups drops to 72%-74%. Likewise, the probability of expanding ineffective groups is largely dependent upon the distribution of effects across the groups. When no groups are effective, the model tends to correctly detect moderate effects as spurious 'highs' and down-weights those estimates leading to less chance of expanding to n=24.

Group	Hist. CBR (%)	All Great	All Null	Half	2 Great	2 Null	Mixed
1	6.25	0.688	0.196	0.574	0.302	0.636	0.475
2	43.50	0.863	0.385	0.511	0.744	0.530	0.782
3	51.10	0.901	0.357	0.820	0.439	0.854	0.488
4	35.40	0.875	0.332	0.488	0.409	0.831	0.628
5	25.00	0.857	0.303	0.777	0.721	0.501	0.764
6	43.50	0.891	0.324	0.481	0.415	0.843	0.470
7	25.00	0.859	0.290	0.766	0.391	0.788	0.608

Table 6 – Probability of expanding from 10 to 24 subjects.

[figure not shown]

Figure 8 – Probability of expanding from 10 to 24 subjects.

The proportion of trials that expand 0, 1, 2, ..., 7 groups are reported (Table 7, Figure 9). When all groups are effective (All Great), typically 5-7 groups expand (on average, 5.934 groups expand). When no groups are effective (All Null), the likelihood of expanding multiple groups decreases greatly, with an average of 2.187 groups expanding.

Groups	All Great	All Null	Half	2 Great	2 Null	Mixed
Average	5.934	2.187	4.417	3.421	4.983	4.215
0	0	0.161	0.013	0.043	0.003	0.019
1	0.002	0.238	0.045	0.105	0.022	0.069
2	0.011	0.235	0.093	0.190	0.048	0.110
3	0.031	0.156	0.140	0.177	0.087	0.124
4	0.057	0.097	0.161	0.182	0.149	0.170
5	0.181	0.065	0.256	0.174	0.274	0.256
6	0.342	0.038	0.202	0.096	0.281	0.170
7	0.376	0.010	0.090	0.033	0.136	0.082

Table 7 – Number of Group Expansions (0, 1, 2,...,7)

[figure not shown]

Figure 9 – Number of Group Expansions (0, 1, 2,...,7)

The proportion of group expansions that declare success, averaged over groups within each trial, is provided in Table 8.

Scenario	Proportion
All Great	0.899
All Null	0.306
Half	0.685
2 Great	0.559
2 Null	0.763
Mixed	0.657

Table 8 – Proportion of group expansions that declare success

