6.3.3 Average Sample Size

The average sample size for each group and for each trial (summing over groups) within each scenario are provided in Tables 9 and 10, and graphically in Figure 10. In the ‘All Great’ scenario, each group is likely to expand and thus the average sample size is close to the maximum per group. In the ‘All Null’ scenario, the average sample size is smaller per group due to early futility stopping and the expansion criteria identifying when enrollment may expand from 10 to 24 subjects.

The average trial size varies from 94.3 subjects to 150.6 subjects. The average trial size reduces as the number of groups that stop enrollment for futility increase. The maximum trial sample size is 168 subjects (full enrollment of 24 subjects within each of 7 groups).

Group	Hist. CBR (%)	All Great	All Null	Half	2 Great	2 Null	Mixed
1	6.25	19.6	12.6	17.8	14.1	18.7	16.5
2	43.50	21.8	14.7	16.5	20.0	16.8	20.6
3	51.10	22.3	14.0	21.1	15.1	21.5	15.8
4	35.40	21.9	13.7	15.8	14.8	21.2	18.1
5	25.00	21.6	13.3	20.4	19.5	15.8	20.2
6	43.50	22.0	13.3	15.2	14.4	21.3	15.1
7	25.00	21.4	12.8	20.0	14.0	20.4	17.3

Table 9 – Average group sample size

Trial Sample Size	All Great	All Null	Half	2 Great	2 Null	Mixed
	150.6	94.3	126.9	111.9	135.6	123.6

Table 10 – Average trial sample size

Average Sample Size

Truth █ Great █ Moderate █ Ineffective

[figure not shown]

Figure 10 – Average group sample size

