The next interim as shown here occurs 13 weeks later at Week 44 (Figure 13). Groups 1, 2, and 3 each have at least 5 subjects with CBR data available. For Group 2, the hierarchical model estimates $\Pr(\pi_g > R_g | \text{data}) = 0.82$, which exceeds the 70% threshold for expansion; thus Group 2 is eligible to continue enrolling beyond 10 subjects (indicated by the green diamond on the plot). Groups 1 and 3 have 0/8 and 4/7 clinical benefit rates, respectively. The $\Pr(\pi_g > R_g | \text{data})$ is 0.38 and 0.65 for these groups, both below the 0.70 sample size expansion threshold and above the 0.20 futility threshold. These groups do not yet meet criteria for expansion or futility and thus must wait for additional data to become available before making decisions. Groups 4, 5, 6, and 7 don't yet have CBR data from at least 5 subjects and each continue to enroll subjects.

[figure not shown]

Figure 13 – Example trial 1, interim 2

6.4.2.3 Example Trial 1, Interim 3

Interim 3 occurs at 57 weeks. Groups 2 (which previously expanded its sample size) continues to enroll subjects. Groups 3 and 4 have clinical benefit rates of 7/10 and 4/6 respectively. The $\Pr(\pi_g > R_g | \text{data})$ is 0.90 and 0.92 for these groups, each above the 0.70 expansion threshold and are therefore eligible to enroll beyond 10 subjects. Group 1 has 0/8 subjects and with a $\Pr(\pi_g > R_g | \text{data}) = 0.43$ remains paused to further enrollment. Group 6 has a CBR of 1/5 and with a $\Pr(\pi_g > R_g | \text{data}) = 0.30$ also pauses further enrollment beyond its currently enrolled 10 subjects. Groups 5 and 7 still don't have CBR data from at least 5 subjects and each continue to enroll more subjects.

[figure not shown]

Figure 14 – Example trial 1, interim 3

6.4.2.4 Example Trial 1, Interim 4

Interim 4 occurs at 70 weeks. Now, groups 2 and 3 are each enrolling beyond 10 subjects. Group 4 which had previously been deemed eligible for expansion based on a CBR of 4/6 now has 10 subjects enrolled, a CBR of 4/9, and $\Pr(\pi_g > R_g | \text{data}) = 0.72$. It still meets the expansion threshold of 0.70 and therefore is still eligible to enroll beyond 10 subjects.

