Group 5 has enrolled 9 subjects, has a CBR of 0/6, and a $\Pr(\pi_g > R_g | \text{data}) = 0.17$. This probability is below the early futility threshold and therefore stops enrollment for futility. Groups 1 and 6 still remained paused at 10 subjects enrolled. Group 7 has 9 subjects enrolled and with a CBR of 2/4 does not have sufficient CBR data available to make a decision about expansion. Therefore, enrollment will pause at 10 for Group 7 until the next interim at which point that decision can be assessed.

[figure not shown]

Figure 15 – Example trial 1, interim 4

6.4.2.5 Example Trial 1, Interim 5

Interim 5 occurs at 83 weeks. Groups 2, 3, and 4 continue to enroll beyond 10 subjects. In addition, Group 7 now has 10 subjects enrolled, a CBR of 3/7, and a $\Pr(\pi_g > R_g | \text{data}) = 0.81$ which is above the 0.70 expansion threshold and becomes eligible to also expand beyond 10 subjects.

Groups 1 and 6 have full follow-up on all subjects (0/10 and 4/10 respectively). Neither of these groups have sufficient evidence to expand beyond 10 subjects.

[figure not shown]

Figure 16 – Example trial 1, interim 5

6.4.2.6 Example Trial 1, Interim 8

Interims 6-7 are not shown here. We next show the results for interim 8 of the trial, which occurs at Week 122. At this point in the trial, Group 2 has complete CBR data for all 24 subjects. For this group, the $\Pr(\pi_g > R_g | \text{data}) = 0.87$ which meets the final success criteria based on a 0.80 threshold. Group 3 has fully enrolled all 24 subjects and is awaiting full follow-up prior to making a decision.

Groups 4 and 7 continue to enroll addition subjects while groups 1 and 6 remain paused to further enrollment.

[figure not shown]

Figure 17 – Example trial 1, interim 8

6.4.2.7 Example Trial 1, Interim 10

Interim 9 is not shown here. We next show the results for interim 10 of the trial, which occurs at Week 148. Now Group 3 has complete CBR data for all 24 subjects. For Group 3, the CBR is 18/24 and the $\Pr(\pi_g > R_g | \text{data}) = 0.98$ which also meets the final success criteria based on a 0.80 threshold.

Group 4 has enrolled 19 subjects, has a CBR of 5/15, and a $\Pr(\pi_g > R_g | \text{data}) = 0.56$. This probability is below the 0.60 post-expansion futility criteria. Therefore, with CBR data not continuing to look promising, Group 4 stops for futility. Group 7 is the only group continuing to enroll subjects into the trial.

[figure not shown]

Figure 18 – Example trial 1, interim 10

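### Protocol 10.4.3 and SAP 2.5.2 stop a cohort's enrolment for success at a posterior above 0.70, where the simulated design expands the cohort and allows no early success stop

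*Protocol*

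**What the plan says.** In Protocol 10.4.3 the Early Success paragraph states that if Pr(π_g > R_g) > 0.70, "then the subgroup will stop enrollment early for success". It adds that at least 5 evaluated patients are needed before a group can be called efficacious. SAP 2.5.2 repeats the paragraph word for word.

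Other parts of the two documents say otherwise:

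- **Protocol 10.4.2, Appendix 4 section 2 and SAP 2.5.2:** "No early stopping for success is allowed".
- **Appendix 4, 5.2:** above 0.70, "then the group is eligible to expand its overall sample size from 10 to 24 subjects". Appendix 4 section 3 says a paused group may restart on the same criterion.
- **Protocol 4.3 and SAP 1.1.3:** meeting the early success criterion is a go decision to keep enrolling, to at most 30. Groups that are neither futile nor eligible to expand pause at 10.
- **The next rule in Protocol 10.4.3:** futility below 0.60, with the condition "A group is only eligible for this post-expansion stopping criterion once the group has expanded to a sample size beyond 10 subjects enrolled".
- **Final success:** declared at a posterior above 0.80 (Protocol 10.4.3, Final Analysis; Appendix 4, 5.4).

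**The concern.** One threshold carries two opposite actions. Protocol 10.4.3 also conflicts with itself. Its interims are announced as assessing futility and sample size expansion, and it has a post-expansion futility rule, yet it contains no rule under which a cohort expands. The sentence on eligibility lasting until the next interim makes sense only for expansion.

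The sample size rationale in Protocol 10.8 and SAP section 3 rests entirely on the Appendix 4 simulations. If the written rule is followed, those simulations describe a different trial. The wording was current at Amendment 1, when initial enrolment was complete in 6 of 7 cohorts and an analysis was awaited to decide on re-opening.

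**Working it through.** **1. The worked example (Appendix 4, 6.4.2).** At interim 2, Group 2 has posterior 0.82, "which exceeds the 70% threshold for expansion; thus Group 2 is eligible to continue enrolling beyond 10 subjects". At interim 3, Group 4 has 4/6 and posterior 0.92 and becomes eligible to expand. At interim 10 it has 5/15 and posterior 0.56, and "with CBR data not continuing to look promising, Group 4 stops for futility". The 10.4.3 wording would have closed Group 4 for success at interim 3.

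**2. Sample size from the documents.** Under the written rule a cohort above 0.70 stops, and one between 0.20 and 0.70 pauses at 10 (Protocol 4.3). No cohort passes 10, so the maximum is 7 × 10 = 70 and the 0.60 rule can never operate. Appendix 4, 6.3.3 gives averages of 94.3 to 150.6, and "The maximum trial sample size is 168 subjects" (7 × 24).

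**3. Where the simulated successes came from.** Table 8 reports the "proportion of group expansions that declare success". I divided the column sums of Table 3 (successes) by those of Table 6 (expansions):

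| Scenario | Table 3 sum / Table 6 sum | Ratio | Table 8 |
|---|---|---|---|
| All Great | 5.341 / 5.934 | 0.900 | 0.899 |
| All Null | 0.670 / 2.187 | 0.306 | 0.306 |
| Half | 3.029 / 4.417 | 0.686 | 0.685 |
| 2 Great | 1.912 / 3.421 | 0.559 | 0.559 |
| 2 Null | 3.804 / 4.983 | 0.763 | 0.763 |
| Mixed | 2.772 / 4.215 | 0.658 | 0.657 |

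Agreement is to about 0.001 throughout. That is what one expects if practically every success came from an expanded cohort. The logic of the design points the same way: a posterior above 0.80 is also above 0.70, so a paused cohort that reached it at an interim would re-open.

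**4. Re-simulation.** Inputs are all from Appendix 4:

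- Historical rates: R_g = 0.5^(6/median PFS in months), e.g. 0.5^(6/1.5) = 0.0625.
- Great effect: +0.7 on the log-odds scale.
- Poisson accrual at 20, 16, 13, 11, 10, 7 and 6 patients a year; 24-week endpoint; no dropout.
- First interim at 5 evaluable or 10 enrolled in any group, then every 13 weeks.
- Dirichlet process α = 2 and τ² ~ IG(3, 0.5). The posterior sums over all cluster partitions, with μ and τ specific to each cluster.
- The μ prior prints as N(0, 1.82). It was run as variance 1.82 and as a standard deviation of 1.80–1.82.

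Ranges cover these readings and separate runs of 800 to 4,000 trials per scenario. Only the action at 0.70 differs between the last two columns; final success needs > 0.80 in both.

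| Quantity | Appendix 4 | Expand at > 0.70 | Stop at > 0.70 |
|---|---|---|---|
| Mean N, All Null | 94.3 | 93.7–94.3 | about 68 |
| Mean N, All Great | 150.6 | 150.1–151.3 | about 67 |
| Success, All Great, SCLC | 0.565 | 0.54–0.58 | 0.44–0.49 |
| Success, All Great, other six | 0.762–0.824 | 0.74–0.83 | 0.64–0.76 |
| False success per cohort, All Null | 0.049–0.126 | 0.05–0.12 | 0.08–0.17 |
| Any false success, All Null | 0.431 | 0.40–0.42 | 0.50–0.52 |

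The expansion reading reproduces the appendix closely. The stated 0.431 comes from 1,000 trials, so its standard error is √(0.431 × 0.569 / 1,000) = 0.016. The stopping reading cannot have produced the appendix figures.

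If crossing 0.70 at an interim were itself treated as declaring efficacy, at least one null cohort would do so in 0.83–0.87 of trials.

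**The case against.** The intended rule is not in real doubt. Early success stopping is excluded three times, Protocol 4.3 treats early success as a reason to continue, and Appendix 4 spells out expansion. The Amendment 1 status text, with cohorts waiting to re-open, fits pause-then-expand, and nothing shows the written rule was ever used. The SAP addendum includes changes made after database lock, so its copy could not steer enrolment. On this view the paragraph is leftover drafting text that needs only a wording correction.

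Most of that stands as a statement of intent, but it does not settle which text governs. Protocol 10.4 defers to Appendix 4 only for the details of the hierarchical model. The SAP says Appendix 4's analysis details are included in its Section 2.5, which is untrue for this rule.

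Three cautions on size also stand. The 70-patient cap needs the pause at 10 from Protocol 4.3, because 10.4.3 states no cap. The rise in any false success is about 10 points within the simulation, but 7 to 9 points against the stated 0.431 (0.50–0.52 less 0.431). Table 8 may simply have been calculated as total successes over total expansions, so the match in step 3 is supporting evidence, not proof. The contradiction does not depend on it.

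**Conclusion.** The concern holds. Both documents state the action at the 0.70 threshold in a form that reverses the simulated design and contradicts their own exclusion of early success stopping. The contradiction follows from the text alone.

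The size is conditional on someone following the written rule with the pause at 10. The trial would then be at most 70 patients, with lower power in every cohort and roughly a one-in-two chance of at least one false success under the global null. The simulated figures assume the Appendix 4 accrual, no dropout and the two readings of the μ prior; the direction is the same under each. Because this is a primary decision rule stated in opposite directions, it must be corrected.

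**What to change.** - **Protocol 10.4.3 and SAP 2.5.2:** replace the Early Success paragraph with the rule in Appendix 4, 5.2. Above 0.70 at the latest interim, with at least 5 evaluable patients, the cohort is eligible to enrol beyond 10, up to 24 in the primary population. Remove the stop-for-success sentence and the reference to calling a group efficacious at this step. State that success is declared only at the final analysis, above 0.80; the basis is Protocol 10.4.2 and the Final Analysis text, not Appendix 4, 5.2.
- **Protocol 10.7 and 10.8, SAP 2.14 and section 3:** change *early success* to *sample size expansion*. In the sample size sentence, keep the two conditions apart: at least 5 evaluable patients for a decision, and a pause at 10 enrolled unless the expansion criterion is met.
- **Tumour types leaving the study for early success:** reconcile this wording in the Protocol summary, Protocol 1.1.2, 2.1, 4.1 and 5.2, and SAP 1.1.1. Where the text says excluded or added, make clear which outcome leads to which action.
- **SAP section 4:** record the correction; it now lists only the analysis-set changes.
- **Clinical study report:** tabulate, for each interim and cohort, the posterior, the rule applied and the action taken.

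The cost is a text correction and one short table. No new data or analysis is needed, and the text then matches the design that was simulated.
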